2.1.3. Additional Estimand

Not applicable.

2.2. Study Design

This is a Phase 4, open-label, multicenter, non-randomized, prospective, single arm study to evaluate the safety and tolerability of lorlatinib in adult participants with unresectable advanced and/or recurrent ALK-positive NSCLC with resistance or intolerance to at least 1 prior ALK inhibitor treatment.

This study will enroll enough participants to ensure that 100 participants are treated with lorlatinib.

Participants will continue with the assigned study treatment until disease progression, participant refusal/lost to follow-up, or unacceptable toxicity. At the end of the study, participants who are on treatment and benefiting from Lorlatinib treatment will be moved to commercially available Lorlatinib (if considered appropriate by the Investigator) as soon as feasible.

3. ENDPOINTS AND BASELINE VARIABLES: DEFINITIONS AND CONVENTIONS

3.1. Primary Endpoint

The primary endpoint is the incidence of AEs. AEs will be graded by the Investigator according to the National Cancer Institute Common Terminology Criteria for Adverse Events (NCI CTCAE) version 4.03 and coded using the Medical Dictionary for Regulatory Activities (MedDRA). The focus of AE summaries will be on treatment-emergent adverse events (TEAEs) defined in section 3.5.1.

3.2. Secondary Endpoints

3.2.1. Confirmed Objective Response Rate (ORR)

Objective Response (OR) based on investigator assessment is defined as CR or PR according to RECIST v1.1 from date of first dose until documented PD or start of new anticancer therapy without regard to discontinuation from treatment. Both CR and PR must be confirmed by repeat assessments performed no less than 4 weeks after the criteria for response are first met. Participants without a CR or PR or with death prior to first post-baseline assessment, inadequate baseline assessment, new anticancer therapy started prior to first post-baseline assessment, and all post-baseline disease assessments missing will be considered as non-responders.

ORR is defined as the percent of participants with best overall response (BOR) as confirmed CR or confirmed PR according to RECIST version 1.1 BOR is defined in section 6.2.1.

3.2.2. Confirmed Intracranial Objective Response Rate (IC-ORR)

Intracranial OR based on investigator assessment is defined as IC-CR or IC-PR according to RECIST v1.1 from date of first dose until documented Intracranial Progressive Disease (IC-PD) or start of new anticancer therapy without regard to discontinuation from treatment. Both

IC-CR and IC-PR must be confirmed by repeat assessments performed no less than 4 weeks after the criteria for response are first met. Participants without IC-CR or IC-PR or with death prior to first post-baseline assessment, inadequate baseline assessment, new anticancer therapy started prior to first post-baseline assessment, and all post-baseline disease assessments missing will be considered as non-responders.

IC-ORR is defined as the percent of participants with intracranial response (ie, best overall intracranial response as confirmed CR or confirmed PR considering only intracranial lesions) relative to participants with CNS metastases at study entry.

3.2.3. Duration of Response (DoR)

DoR is defined as the time from the first documentation of objective tumor response (confirmed CR or confirmed PR) to the first documentation of disease progression or death due to any cause, whichever occurs first. The censoring rules for DOR are presented in section 6.2.3.

3.2.4. Intracranial Duration of Response (IC-DoR)

IC-DoR is defined as the time from the first documentation of an intracranial objective response in the subgroup of participants with brain metastasis at baseline. The censoring rules for DoR will be used for IC-DoR.

3.3. Other Endpoint

Not applicable.

3.4. Baseline Variables

Start and end dates of study treatment:

The date of first dose (start date) of study treatment is the earliest date of non-zero dosing of the study drug.

The date of last dose of study treatment is the latest date of non-zero dosing of the study drug.

Definition of baseline:

No windowing will be applied when defining baseline, except as noted in Section 5.2.8 for tumor assessments. Any deviations from the protocol specified window will be documented as protocol deviations. A separate definition of adequate baseline will be provided for tumor assessment related antitumor activity endpoints.

For antitumor activity analyses and baseline characteristics associated with tumor assessments the last assessment prior to treatment start date will serve as the baseline assessment.

For safety (including laboratory, vital signs and Eastern Cooperative Oncology Group (ECOG) performance status) the last assessment performed on or prior to date of the first

dose of study treatment will serve as the baseline assessment. If there are no observations meeting these criteria, then baseline is considered missing.

Participants who start treatment and discontinue from the study on the same day may have two different sets of data collected on study day 1 (one during study and one in the End of Treatment (EOT) visit. Data reported at the EOT visit are not eligible for baseline selection.

Triplicate electrocardiograms (ECGs) are collected pre-dose; therefore, the baseline for each ECG measurement is the average of the latest pre-dose triplicate measurements. Unscheduled assessments will not be included in the calculation of the average.

3.5. Safety Endpoints

Safety endpoints will be summarized based on the on-treatment period unless otherwise specified. Safety data collected outside the on-treatment period as described below will be listed but not summarized.

3.5.1. Treatment Exposure

On-treatment is defined as the time from the first dose of study treatment through end of safety follow-up period, ie 35 days after discontinuation of treatment, or start of new anticancer therapies (follow-up systemic therapy, follow-up radiation therapy to target or non-target lesions or follow-up surgery to target or non-target lesions), whichever occurs first. Adverse events occurring on the same day as the first dose of study treatment will be considered to have occurred during the on-treatment period.

An adverse event is considered treatment emergent (TEAE) if:

- the event occurs for the first time during the effective duration of study treatment and was not observed prior to the start of study treatment (e.g., during screening), or
- the event was observed prior to the start of study treatment but increased in severity during the effective duration of study treatment.

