## 4.1. Inclusion Criteria

Participant eligibility should be reviewed and documented by an appropriate member of the Investigator's study team before participants are included in the study.

Participants must meet all of the following inclusion criteria to be eligible for enrollment into the study:

- 1. Evidence of histologically or cytologically confirmed diagnosis of unresectable advanced and/or recurrent NSCLC that carries an ALK rearrangement, as detected by an appropriate test.
- 2. Disease progression or intolerance to 1 previous treatment with ALK TKI. participants may have also had prior chemotherapy for their advanced and/or recurrent disease.
- 3. Participants with asymptomatic CNS metastases (including participants controlled with stable or decreasing steroid use within the last 2 weeks prior to study enrollment) will be eligible.
- 4. Age  $\geq 18$  years.
- 5. Eastern Cooperative Oncology Group (ECOG) performance status (PS) 0, 1, or 2.
- 6. Adequate hematologic and renal function as defined as:
  - a. Absolute neutrophil count (ANC)  $\geq 1,000/\text{mm}^3$ ;
  - b. Platelets  $\geq$  50,000/mm^3;
  - c. Hemoglobin  $\geq 8 \text{ g/dL}$ ;
  - d. Estimated creatinine clearance  $\geq$ 30 mL/min as calculated using the method standard for the institution.
- 7. Adequate liver function, including:
  - a. Total serum bilirubin  $\leq 1.5 \times$  upper limit of normal (ULN);
  - b. Aspartate aminotransferase (AST) and alanine aminotransferase (ALT)  $\leq 2.5 \times \text{ULN} (\leq 5.0 \times \text{ULN} \text{ in case of liver metastases}).$
- 8. Adequate pancreatic function, including:
  - a. Serum total amylase  $\leq 1.5 \times ULN.*$
  - b. Serum lipase  $<1.5 \times ULN$ .

\*if total amylase >1.5  $\times$  ULN, but pancreatic amylase is within the ULN, the participant may be enrolled.

- 9. Acute effects of any prior therapy resolved to baseline severity or to CTCAE Grade <1 except for AEs that in the Investigator's judgment do not constitute a safety risk for the participant.
- 10. Systemic anticancer therapy completed within a minimum of 5 half-lives of study enrollment (unless clinically meaningful tumor flare per discretion of the Investigator, in which discussion with the Sponsor is warranted).
- 11. Evidence of a personally signed and dated informed consent document indicating that the participant (or a legally acceptable representative) has been informed of all pertinent aspects of the study.

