## 8.2. Reporting Period

For AEs and SAEs, the active reporting period to Pfizer or its designated representative begins from the time that the participant provides informed consent, which is obtained prior to the participant's participation in the study, ie, prior to undergoing any study-related procedure and/or receiving investigational product, through and including at least 28 calendar days and no more than 35 days after the last administration of the investigational product. SAEs occurring to a participant after the active reporting period has ended should be reported to the Sponsor if the Investigator becomes aware of them; at a minimum, all SAEs that the Investigator believes have at least a reasonable possibility of being related to study drug are to be reported to the Sponsor.

If a participant begins a new anticancer therapy, the AE reporting period for nonserious AEs ends at the time the new treatment is started. Death must be reported if it occurs during the SAE reporting period after the last dose of investigational product, irrespective of any intervening treatment.

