###  Primary Endpoint

AEs will be graded by the Investigator according to the CTCAE version 4.03 and coded using the MedDRA. The focus of AE summaries will be on TEAEs, those with an initial onset or increasing in severity after the first dose of study medication up to at most 35 days post last dosing date or the date of initiation of a new anticancer therapy. The number and percentage of participants who experienced any AE, SAE, treatment-related AE, and treatment-related SAE will be summarized.

Adverse events leading to death or discontinuation of study treatment, events classified as NCI CTCAE version 4.03 Grade  $\geq$ 3, study drug-related events, SAEs, dose reductions due to AEs, and temporary and permanent discontinuations due to AEs will be summarized.

Detailed information collected for each AE will be listed with a description of the event, duration, whether the AE was serious, intensity, relationship to study treatment, action taken, and clinical outcome.

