6. ANALYSES AND SUMMARIES

6.1. Primary Endpoint

6.1.1. Adverse Events

6.1.1.1. Main Analysis

Analysis set: Safety: All enrolled participants who take at least 1 dose of Lorlatinib **Analysis methodology**:

- AE incidence rate is the number of patients with any AE occurring at least once in the study population.
- All Adverse Events (AEs) will be coded using the MedDRA.
- All analyses will be based on treatment emergent events unless otherwise specified. Treatment emergent is defined in Section 3.5.1.

Intercurrent events and missing data:

• All data after the intercurrent event "start of subsequent anticancer therapy (-1 day)" or "35 days after treatment discontinuation" will be excluded from summaries but will be listed regardless of dosing interruptions or dosing compliance.

Summaries used for reporting:

- High-level summaries of adverse events (both All Causality and Treatment Related) will include the number and percent of participants with:
 - o Any Adverse Event;
 - o Serious AE;
 - o Adverse Events with CTCAE Grade 3-4;
 - o Grade 5 events;
 - o AEs associated with dose interruptions;
 - o AEs associated with dose reductions;
 - o AEs associated with withdrawal;

Additionally, the number of events reported for each of the categories above will be provided. Each unique adverse event at the PT level for a participant is included in the count. Seriousness, relatedness, toxicity grade, action taken (interruption, reduction, and withdraw) are as reported by the investigator on the adverse event CRF.

- Summaries by System Organ Class (SOC) and PT in decreasing frequency will be provided for:
 - o Treatment Emergent Events by Maximum Toxicity Grade (All Causality);
 - Treatment Emergent Events by Maximum Toxicity Grade (Treatment Related);

- Serious Treatment Emergent by Maximum Toxicity Grade Events (All Causality);
- Serious Treatment Emergent by Maximum Toxicity Grade Events (Treatment Related);

An event will be considered treatment related if the investigator considered the event related to the study drugs or this information is unknown.

Clustered adverse events will be summarized by maximum CTCAE grade and
causality (all-causality and treatment-related) together with other adverse events.
Adverse Events pertaining to each cluster will be summarized separately, by cluster.
The clustered events are described in a list in the product's Safety Review Plan
maintained by the Sponsor.

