6.5. Baseline and Other Summaries and Analyses

6.5.1. Baseline Summaries

• Demographic and Physical Characteristics

The following demographic and baseline characteristics will be summarized by number and percentage:

- o Gender (male, female)
- o Age (18-<45; 45- <65; >65)
- ECOG Performance status

Age (continuous) and weight (kg) will be summarized with descriptive statistics (mean, median, Std Dev, minimum, and maximum, inter quartile range).

Disease Characteristics

The following baseline disease characteristics will be summarized by number and percentage:

Measurable disease at baseline (yes/no) (see Section 5.2.5)
 PFIZER CONFIDENTIAL

^a more than 26 weeks after last adequate tumor assessment.

- o Involved tumor sites at baseline.
- O Number of sites of disease at baseline $(1, 2, \ge 3)$

Involved tumor sites at baseline will be derived from target and non-target lesions at baseline. Each participant will be counted once per organ. Similarly, number of sites of disease at baseline will be derived by counting the number of unique organ sites from target and non-target lesions at baseline. "Other" will be counted as one organ site.

• Medical History

Medical history will be coded using the most current version of MedDRA and summarized by MedDRA's SOC and PT. Each participant will be counted only once within each PT or SOC. Summaries will be ordered by primary SOC and PT in descending order of frequency. Separate summaries will be provided for past and present conditions.

• Prior Anticancer Treatments

Prior anticancer treatments include systemic therapy, radiation, and surgery. The number and percentage of participants in each of the following anticancer therapy categories will be tabulated:

- o Participants with at least one type of prior anticancer treatment;
- o Participants with at least one prior anticancer drug therapy;
- o Participants with at least one prior anticancer radiotherapy;
- o Participants with at least one prior anticancer surgery.

Prior anticancer drug therapy will be summarized as follows based on the number and percentage of participants:

- o Number of prior anticancer therapy regimens: missing $/1/2/3/\ge 4$;
- o Number of participants who received prior chemotherapy
- Number of participants who received 1st generation (Crizotinib) or 2nd generation (Alectinib, Certinib or Brigatinib) ALK Inhibitor (ALKi) as Prior ALKi

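### The TEAE rule has no route for an event that resolves before first dose and recurs at the same or a lower grade, so such recurrences leave the treatment-emergent AE tables although they fall within the primary estimand

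*SAP*

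**What the plan says.** SAP 3.5.1 gives two routes to treatment-emergent status. By the first, the event occurs for the first time on treatment and "was not observed prior to the start of study treatment (e.g., during screening), or" the second route applies, under which "the event was observed prior to the start of study treatment but increased in severity during the effective duration of study treatment". The test is whether the event was seen before, not whether it was ongoing at first dose. Screening is given as an example and no look-back limit is set.

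The protocol summary (Analysis of Primary Endpoint) and Protocol 9.6 use the same two routes: TEAEs are "those with an initial onset or increasing in severity after the first dose of study medication".

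SAP 6.1.1.1 then applies the filter throughout the primary analysis: "All analyses will be based on treatment emergent events unless otherwise specified". No exception is made for recurrences.

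The primary estimand (SAP 2.1.1) is wider. Its variable is whether any AE occurs at least once between first dose and 35 days after the last dose, or the day before a new anticancer therapy. It does not mention treatment emergence.

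Four other provisions bear on who is exposed to the rule:
- Protocol 4.1, inclusion 2, admits participants with "Disease progression or intolerance to 1 previous treatment with ALK TKI".
- Inclusion 9 asks for "Acute effects of any prior therapy resolved to baseline severity or to CTCAE Grade <1 except for AEs" that the Investigator judges not to be a safety risk.
- AE reporting "begins from the time that the participant provides informed consent" (Protocol 8.2), and screening falls within the 28 days before first dosing (Protocol 6.1).
- Medical history is coded in MedDRA, and "Separate summaries will be provided for past and present conditions" (SAP 6.5.1).

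**The concern.** Safety and tolerability are the primary objective, and some participants enter because they could not tolerate an earlier ALK inhibitor. Whether an earlier toxicity returns on lorlatinib is therefore a natural question for the AE tables. Under the written rule, a toxicity that was recorded after consent, cleared before first dose and came back at the same grade is not a TEAE, even if the Investigator calls it serious and related.

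It would then be missing from the summaries by SOC and preferred term, the serious and treatment-related summaries, the AESI summaries, and the summaries of AEs associated with interruption, reduction or withdrawal (SAP 6.1.1.1). The treatment-emergent tables for basic results (SAP 6.1.1.2) use the same filter. The error has one direction: a tabulated rate can be too low, never too high.

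**Working it through.** **1. Apply the two routes to each possible history.**

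| Before first dose | On treatment | First route (new) | Second route (worse) | TEAE as written | New occurrence in estimand window |
|---|---|---|---|---|---|
| Never seen | Occurs | Yes | – | Yes | Yes |
| Ongoing at first dose | Unchanged | No | No | No | No |
| Ongoing at first dose | Worsens | No | Yes | Yes | Yes |
| Seen, resolved | Recurs at higher grade | No | Yes | Yes | Yes |
| Seen, resolved | Recurs at same or lower grade | No | No | **No** | **Yes** |

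Only the last row separates the tabulated primary analysis from the estimand. For an event recorded between consent and first dose the exclusion follows directly from the wording. For toxicity that ended before consent and sits in medical history, the SAP does not say whether it counts as having been observed.

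**2. Reproduce the plan's precision figure.** Protocol 9.2 gives a maximum standard error of 0.05 with 100 participants. SE = √(p(1−p)/n), largest at p = 0.5: √(0.25/100) = 0.05. This agrees.

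**3. Size per affected participant.** Suppose x of 100 participants have a given term on treatment, and for k of them the only on-treatment occurrence is a same-or-lower-grade recurrence. The tabulated rate is then (x − k)/100. For x = 20, the full rate is 20% (Wilson 95% interval 13.3 to 28.9) and SE = √(0.2 × 0.8/100) = 0.040.

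| k | Tabulated rate | Wilson 95% interval | Shift ÷ SE (0.040) |
|---|---|---|---|
| 1 | 19% | 12.5 to 27.8 | 0.25 |
| 3 | 17% | 10.9 to 25.5 | 0.75 |
| 5 | 15% | 9.3 to 23.3 | 1.25 |

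**4. How large k might be.** The documents give no figure, so this is assumption only. If 10 to 30 participants enter for intolerance, and 10% to 30% of them have an event that is recorded in screening, resolves and recurs at no higher grade, then k runs from 10 × 0.10 = 1 to 30 × 0.30 = 9 across all terms together. If medical history also counts as observed, a wider range is possible: 5% to 30% of participants with a resolved toxicity, recurring at the same grade in 10% to 50% of them, gives 100 × 0.05 × 0.10 = 0.5 to 100 × 0.30 × 0.50 = 15. The upper ends are hard to defend for a screening window of about 28 days. They would also have to fall in one preferred term to shift that term's rate by the full amount.

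**5. What the filter does not touch.** These outputs are not written with the TEAE filter:
- AE listings (SAP 6.1.1.1)
- Discontinuations from treatment due to AEs (SAP 6.5.2.1)
- Dose reductions and interruptions with reasons (SAP 6.5.3.2)
- Laboratory grades, shift tables and liver-test categories (SAP 3.5.3 and 6.6.1)
- Vital signs and ECG (SAP 6.6.2 and 6.6.3)

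**The case against.** Three arguments on the other side have force.

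First, the wording may permit a kinder reading. SAP 5.3.2.1 speaks of a series of similar events, which suggests that a recurrence is a separate record with its own onset. SAP 5.3.3 mentions a baseline grade for pre-treatment AEs, and SAP 3.4 sets the safety baseline at the last assessment on or before first dose. On that logic a resolved event has no grade at baseline, any recurrence is an increase, and nothing is lost. But SAP 5.3.2.1 governs date imputation and SAP 5.3.3 governs missing grades. Neither they nor SAP 3.4 says how a resolved AE is to be classed, and SAP 3.5.1 asks only whether the event was seen before. The gap stays open.

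Second, the exposed group is narrow. AE collection starts at consent, screening is short, and inclusion 7, 9 and 10 (liver function, resolution of earlier effects, washout) mean that much intolerance toxicity will have ended before consent. This stands, and it keeps the likely count low. It also means that the silence on medical history matters.

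Third, a reader might infer that a recurring toxicity vanishes from every safety output. The documents do not support that. A recurrent Grade 3 transaminase rise with a dose hold would still appear in the liver-test and shift summaries and among the dose interruptions. Symptomatic events have less cover: the CNS AESIs of SAP 3.5.2 (mood, speech, cognition) have no laboratory table behind them, and a listing does not replace a tabulated rate.

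**Conclusion.** The point holds as a gap in the definition that makes the treatment-emergent AE tables narrower than the primary estimand. It is certain for events recorded between consent and first dose that resolve and recur at the same or a lower grade, and unsettled for events known only from medical history.

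The size is 1 percentage point per affected participant for the term concerned. The number affected is unknown and probably small. Two stronger conclusions should not be drawn. The any-AE rate is not generally understated, because it changes only for a participant with no other TEAE. Nor do the documents show a shift beyond the plan's 0.05: that would need more than five affected participants in one term, and no source supports such a count.

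The change is still worth making. The error is one-directional, it falls on the primary safety tables, and the population includes participants already known to have had toxicity on a related drug.

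**What to change.** Replace the two routes in SAP 3.5.1 with wording such as: an AE is treatment emergent if (a) its onset is on or after the date of first dose and within the on-treatment period, including recurrence of an event that had resolved before first dose; or (b) it was ongoing at first dose and worsens during the on-treatment period relative to its grade at first dose. Add that an entry in medical history does not by itself exclude an on-treatment event. Using the on-treatment period, which SAP 3.5.1 defines, also removes the undefined reference to an effective duration of treatment. The first-dose reference matches the safety baseline in SAP 3.4.

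Align the protocol summary (Analysis of Primary Endpoint) and Protocol 9.6.

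The cost is SAP text and programming, with no new data. Some intermittent background symptoms that return unchanged will now be counted, so AE rates may be slightly higher. Protocol section 9 requires an amendment for a major change to the primary endpoint definition or its analysis, and amendments need IRB/EC approval (Protocol 12.1). The sponsor would have to decide whether this change is major in that sense.
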